JHM IRB - eForm A – Study Protocol & Analysis Plan

- Use the section headings to write the JHM IRB eForm A, inserting the appropriate material in each. If a section is not applicable, leave heading in and insert N/A.
- When submitting JHM IRB eForm A (new or revised), enter the date submitted to the field at the top of JHM IRB eForm A.

Title: Sleep Disordered Breathing in Marfan Syndrome- Susceptibility and Hemodynamics

NCT No: NCT03985657

Date: December 16th, 2019

[figure not shown]
1. Study Procedures

- a. Study design, including the sequence and timing of study procedures
(Distinguish research procedures from those that are part of routine care).

Study Design/Protocol:

Individuals interested in our study will complete a basic telephone or in-person health screen to verify inclusion/exclusion criteria followed by consenting, history and physical and then sleep studies as outlined in the Figure. Qualifying individuals will come into the lab for the purpose of obtaining informed consent and completing a history and physical. Participants will then be admitted to the sleep laboratory at the Johns Hopkins Bayview Clinical Research Unit for a contiguous or separated two night stay. The first two hours will be required initially for set-up and anthropometric measurements, and the remainder of the night will be spent monitoring and recording sleep and breathing patterns as described below and in the Study Procedures section.

Figure: Study Design

Baseline Night: Participants will undergo an overnight polysomnography (PSG). The parameters monitored include electroencephalogram (EEG), electrocardiogram (ECG), electro-oculogram (EOG), thoraco-abdominal movements, submental electromyogram (EMG), pulse oximetry, continuous blood pressure monitoring (portable probe worn on the finger), chest movement activity (measured by bio-impedance electrodes placed on the chest) and airflow using a pneumotachograph.

Physiology Night: During this night, continuous positive airway pressure (CPAP) will be administered via a nasal mask. In the first 90-120', nasal pressure will be titrated until non-flow limited breathing is achieved and UAO eliminated. The pressure at non-flow limited breathing is considered the ideal treatment pressure and participant will remain at this pressure for the rest of the night. Pressure and airflow data from the titration portion will be used to calculate the P_{crit} ^{10,11,12}. The standard PSG parameters listed above will also be assessed on this night.

In either night, you may receive a sleep aid (Benadryl) if needed to aid sleep initiation.

Additional measurements: Participants will undergo arterial pulse wave analysis (using the EndoPAT; described at end of section) the morning after the baseline and physiology study. On one of the nights, pleural pressure changes will measured continuously using an esophageal catheter (see description of procedure below).

Pressure Catheter: A thin tube (about the thickness of a strand of spaghetti) will be placed through the participant's nose into the food tube (esophagus) after numbing the inside of the nose with some numbing medicine (such as lidocaine). This tube allows us to measure pressure changes in the lungs. This procedure will be carried out on both the baseline and physiology nights.

Bio-impedance measurement: Three EKG patches will be placed horizontally on the chest at the level of the armpit. The EKG patches will be connected to an external bio-impedance monitoring device which allows us to quantify respiratory effort similar to the esophageal pressure swings. This procedure will be carried out on both the baseline and physiology nights.

Objective snoring assessment: A mobile device with a microphone will be placed approximately 60cm from the participant to record snoring sounds.

Blood Test: Following, the sleep studies, a venous blood sample will be collected for serum biomarkers of aortic wall stress.

Peripheral arterial tonometry (EndoPAT): A blood pressure cuff is placed on the non-dominant arm while the participant is in the supine position; the contralateral arm is used for control comparisons. Measurements will be taken for 5 minutes before, 5-min during occlusion of the brachial artery and for 5 minutes upon release of the cuff. The occlusion will be achieved by

inflation of the automated cuff 50 mmHg above systolic blood pressure. Endothelium-mediated vasodilation is assessed using a finger pulse wave amplifier (a probe worn on one finger).

Randomization: It is documented that in the research setting sleep structure is altered specifically in the first sleep session due to exposure to a new sleep environment. Studies with

Date: December 16th , 2019

Principal Investigator: [name], MPH

~~multiple sleep study nights~~ are often confounded by this first night effect phenomenon ¹⁶. To prevent this potential confounding effect, we will ensure that the order in which participants are assigned to a baseline and physiology night study is randomized. So that the findings in either night will not be attributed in part to the sequence in which the visits occurred.

2. Study Statistics

a. Analyses and Sample Size:

Specific Aim 1:

- a. The sample size for this aim is designed to detect differences in P_{crit} between matched groups. Our published data indicate a ΔP_{crit} of 1 ± 0.9 cmH₂O as significant clinically. Therefore sample size calculations estimate 15 subjects each in MFS and control groups necessary to detect a baseline difference in P_{crit} of 1.0 ± 0.9 cmH₂O with a power of 85% (two-sided test, with α type 1 error = 0.05). These considerations lead us to propose a final sample size of 15 MFS patients and 15 non MFS controls (n=30 participants). We will recruit 30 MFS and 30 non MFS controls in total to allow for attrition, sub group analyses and missing data.
- b. Overnight UAO exposure will be determined by 1) apnea-hypopnea-index (AHI) and b) a composite measure of pleural pressure swings during UAO. Wilcoxon non-parametric t-test comparisons will be used to determine differences in these parameters between MFS and matched controls.

Specific Aim 2:

- a. We have estimated the required sample size of 15 in each group to see a difference of 10 units in hemodynamic parameters between groups at 90% power and a significance alpha level of 0.05 ¹⁵. We will compare hemodynamics (heart rate and pulse pressure) at baseline vs CPAP in pair wise t-test comparisons after accounting for sleep stage, body position and respiratory phase.

Stratified regression analyses will be used to determine whether the magnitude of hemodynamic parameters are predicted by genotype (MFS vs non MFS) at baseline and CPAP after accounting for sleep stage, body position and respiratory phase.

- b. We will utilize descriptive techniques such as scatter plots, correlation analyses to explore the relationship between hemodynamic response to UAO and measures of aortic disease progression (aortic diameter, rate of aortic diameter increase in the past five years and augmentation index) in MFS. This relationship will also be examined using a multivariate

Date: December 16th , 2019

Principal Investigator: [name], MPH

Application No.: IRB00157403

- c. regression model adjusting for age, sex and body surface area. Augmentation index will be obtained from the morning EndoPAT measurements (see section 2) and aortic parameters will be obtained from the protocol; **IRB00157483**.

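### Night order is randomised against a first-night effect, but no allocation method is stated and no listed analysis includes order: an optional gain in precision

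*Combined protocol and SAP*

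**What the plan says.** Section 1 (Randomization) explains that "sleep structure is altered specifically in the first sleep session due to exposure to a new sleep environment", and responds that "we will ensure that the order in which participants are assigned to a baseline and physiology night study is randomized". It does not describe how: no method, ratio, blocking or stratification by group is given.

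Order can enter the results in two ways. Pcrit comes from one night only, the physiology night ("Pressure and airflow data from the titration portion will be used to calculate the" Pcrit), so it enters the group contrast through the share of each group having that night first. The Aim 2a night comparison is within person: "We will compare hemodynamics (heart rate and pulse pressure) at baseline vs CPAP in pair wise t-test comparisons". There, order enters every individual difference.

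The listed analyses in section 2 are:

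- **Aim 1a:** a Pcrit comparison between matched groups, with no covariates named.
- **Aim 1b:** "Wilcoxon non-parametric t-test comparisons will be used to determine differences in these parameters between MFS and matched controls".
- **Aim 2a:** the paired tests and stratified regressions, accounting for sleep stage, body position and respiratory phase.
- **Aim 2b:** a "regression model adjusting for age, sex and body surface area".

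None contains night order. The final sample size is 15 per group. The larger figure is a recruitment target: "We will recruit 30 MFS and 30 non MFS controls in total to allow for attrition, sub group analyses and missing data".

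**The concern.** The plan identifies a nuisance factor and randomises it, then leaves it out of every model. Variation due to order therefore stays in the residual error. With 15 per group, simple randomisation can also leave the two groups with noticeably different shares having the physiology night first. The stake is some power in a small study, which a blocked order list and one extra model term could recover. The two steps depend on each other: blocking without modelling makes the tests conservative, and modelling without blocking wastes information if there is no order effect.

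**Working it through.** **Inputs from the documents.** Pcrit: difference 1.0 cmH2O, SD 0.9, two-sided alpha 0.05, power 85%, 15 per group. Aim 2a: 10 units, 90% power, alpha 0.05, 15 per group, no SD stated.

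**Reproducing the plan's figure.** n = 2(1.960 + 1.036)² × 0.9² / 1.0² = 14.5, so 15 per group, as stated. The exact t-test power at 15 is 83.6%, which is the reference below.

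**Back-solved SD for Aim 2.** For 10 units at 90% power, 15 pairs imply an SD of the within-person difference of 11.10. Read as a two-group comparison, as the sample-size sentence has it ("We have estimated the required sample size of 15 in each group to see a difference of 10 units in hemodynamic parameters between groups"), the implied SD is 8.15.

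**Assumptions not in the documents.** Simple 1:1 randomisation of order, and a first-night minus second-night shift, the same for everyone, of q = 0.3/0.5/0.9 cmH2O (Pcrit) or p = 3/5/8 units (Aim 2). The top values are large: 0.9 is one SD, and 8 is 80% of the target difference.

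**Formulas, with the planning SD excluding order variance.**

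- Pcrit, order ignored: SE = √(0.9² + q²/4) × √(2/15). Blocked and modelled: SE = 0.9 × √(2/15) = 0.329.
- Paired test, order ignored: SE = √(11.10² + p²) / √15. Blocked and modelled: SE = 11.10 / √15 = 2.87.

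Power at 15 per group:

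| Comparison | Shift | SE, order ignored | Power, order ignored | Power, blocked and modelled |
|---|---|---|---|---|
| Pcrit | 0.3 | 0.333 | 83% | about 83.5% |
| Pcrit | 0.5 | 0.341 | 81% | about 83.5% |
| Pcrit | 0.9 | 0.367 | 75% | about 83.5% |
| Aim 2 paired | 3 | 2.97 | 88% | about 90% |
| Aim 2 paired | 5 | 3.14 | 84% | about 90% |
| Aim 2 paired | 8 | 3.53 | 75% | about 90% |

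Read as a between-group comparison (SD 8.15), Aim 2 gives 89/87/83% against 90%.

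**If the planning SD already contains order variance.** Order ignored keeps about 84% (Pcrit) and 90% (paired). Blocking and modelling would raise these to about 84/86/92% and 92/95/99+%.

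**Validity.** With simple randomisation and order ignored, simulated type I error of the paired test is 4.9 to 5.2%. The between-group difference in the share having the physiology night first has SD √(0.5/15) = 18.3 percentage points, and a gap of 20 points or more has probability 36%. At q = 0.5 such a gap moves the Pcrit difference by 0.20 × 0.5 = 0.10 cmH2O. That movement is random and is already carried in the standard error.

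**Half-measures at 15.** Blocked but not modelled, type I error falls to about 4.4/3.4/1.8% (paired) and 4.8/4.2/3.0% (Pcrit). Modelled but not blocked, the paired test drops from 90.0% to about 87% power if there is no order effect.

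**Aim 1b at 15 per group** (assumed group shift 1.11 SD; order effect 0.33/0.56/1.0 SD). Unmatched: rank-sum 81/79/72% against 80/80/81% for an order-stratified (van Elteren) test. Individually matched, with an assumed within-pair correlation of 0.3: signed-rank 90/88/80% when pair members have independent orders, against 91% when they share one.

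**At 30 per group, all analysable.** The gain is 98.3% to 98.9% for Pcrit at q = 0.5, and 99.1% to 99.7% for the paired test at p = 5, so under 1 point. For the paired test it is 97.3% to 99.7% at p = 8, and about 92% to 99.7% at a shift of one SD of the difference (11.1 units), about 7.5 points.

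**The case against.** The strongest reply is that nothing is broken. Randomisation has one stated purpose, that findings should not be attributable to visit sequence, and randomising order achieves it. Using order to reduce variance is a further aim that the plan never set. That stands as to validity, but it does not remove a cheap gain on a factor the plan itself names.

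A reader might infer that the results will be confounded by the first night, or that order was not blocked. The documents support neither. Chance imbalance under randomisation is not bias, and the plan is silent on method. If order is in fact blocked, the order-ignored power figures do not describe this trial and the conservative type I errors apply instead.

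The shift itself is assumed. The plan says only that sleep structure changes; it claims no effect on Pcrit, heart rate or pulse pressure. Aim 2a already accounts for sleep stage, the variable closest to that mechanism. If this absorbed half the shift, the paired figures at 15 would be 89.3/88.7/86.3% against about 89.5%. The two nights may also be contiguous or separated, so a common shift is a simplification. These limits all stand and are why the change is optional.

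**Conclusion.** The point holds as one of precision. Order is randomised by an unstated method and appears in no listed analysis. At the final sample of 15 per group, blocking and modelling order is worth roughly 1 to 9 power points for Pcrit and 2 to 15 for the paired Aim 2 test across the assumed shifts, if the planning SDs exclude order variance. If they include it, the plan loses nothing against its own target. The documents do not say which applies, so a conclusion that the study is underpowered because of order is not supported.

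Nor should the matter be dismissed on the strength of 30 per group. That is the recruitment target, and the gain there is small only for moderate shifts. The sizes rest on the assumed shifts, 1:1 simple randomisation and, for Aim 2, a back-solved SD.

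**What to change.** Optional. State the allocation method, and randomise night order 1:1 in permuted blocks within the MFS and control groups. Add night order as a fixed effect to the Pcrit comparison, the Aim 2a baseline-versus-CPAP comparison and the Aim 2a regressions. Adopt blocking and modelling together.

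For Aim 1b, first state whether the Wilcoxon test is the matched-pair or the unmatched form. If unmatched, use an order-stratified rank test or a regression with an order term. If controls are individually matched, give both members of a pair the same order and keep the signed-rank test; a first-night shift common to both groups then cancels within the pair. The exploratory Aim 2b models need no change.

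The cost is a blocked order list, a few sentences of analysis text and one degree of freedom per model. If there is no order effect, the loss at 15 per group is about 0.2 to 0.5 power points for the models, about 1.5 for the stratified rank test (82.1% to 80.6%), and essentially none for the signed-rank test with shared order. Pair-shared order also requires carrying each participant's assigned order over to the matched partner, a small logistical burden.

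### Does Aim 1's sample size use the spread of a Pcrit difference where it needs the between-person SD?

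*Combined protocol and SAP*

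**What the plan says.** Everything on this point is in section 2a (Analyses and Sample Size), Specific Aim 1.

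- Item a sets the purpose: "The sample size for this aim is designed to detect differences in P_{crit} between matched groups".
- It gives the source of the effect: "Our published data indicate a ΔP_{crit} of 1 ± 0.9 cmH₂O as significant clinically".
- It states 15 subjects in each group as "necessary to detect a baseline difference in P_{crit} of 1.0 ± 0.9 cmH₂O with a power of 85" per cent, with a "two-sided test, with α type 1 error = 0.05".
- It sets the number to analyse and the number to enrol separately. It will "propose a final sample size of 15 MFS patients and 15 non MFS controls (n=30 participants"), and then: "We will recruit 30 MFS and 30 non MFS controls in total to allow for attrition, sub group analyses and missing data".
- Item b names a test only for AHI and the pleural pressure measure: "Wilcoxon non-parametric t-test comparisons will be used to determine differences in these parameters between MFS and matched controls".

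The documents do not say whether ± 0.9 is an SD or a standard error, or whether the published ΔPcrit compares two groups or two conditions in the same person. They do not name the Pcrit test or say whether matching is one-to-one or by group. They give no separate SD of Pcrit for either group.

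**The concern.** A two-sample calculation needs the SD of Pcrit between people within a group. Both sentences that carry the calculation attach 0.9 to a difference instead. The two quantities can be far apart. The SD of a change within a person leaves out the stable differences between people, so when repeated values are highly correlated it can be much smaller than the between-person SD. Putting it into a two-group formula would then understate the number needed.

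Pcrit is the only variable on which Aim 1 is sized. If the true between-person SD were well above 0.9, a study of 15 per group could easily miss a real difference of 1.0 cmH₂O, and a null result could be misread as equal airway collapsibility in Marfan patients and controls. The word matched adds to the doubt, because a one-to-one design would be sized on the SD of the pair difference and analysed with a paired test.

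**Working it through.** **Inputs from section 2a, Specific Aim 1, item a:** difference δ = 1.0 cmH₂O; spread 0.9 cmH₂O; two-sided α = 0.05 (z = 1.960); power 85% (z = 1.036); 15 per group; 30 per group recruited.

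**Step 1. Reproduce the plan's figure, with 0.9 as the common between-person SD in an unpaired test.**

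n per group = 2 × (1.960 + 1.036)² × (0.9/1.0)² = 14.5, rounded up to **15**.

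Power at 15 (normal): δ/(SD × √(2/n)) = 1.0/(0.9 × √(2/15)) = 3.043, and Φ(3.043 − 1.960) = **86.1%**.

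Exact two-sample t (noncentral t, 28 df): **83.6%** at 15 and 86.0% at 16. The shortfall of 1.4 points, or one person per group, is the usual gap between the normal formula and the t-test.

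**Step 2. Try 0.9 as the SD of a matched-pair difference in a paired test.**

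n = (1.960 + 1.036)² × 0.9² = 7.3, so 8 pairs by the normal formula. The exact paired t-test gives 83.0% at 9 pairs, 87.7% at 10 and **97.9%** at 15. This does not reproduce 15 at 85%, and under it the plan has more people than it needs.

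**Step 3. Try 0.9 as the SD of a within-person change, with the groups compared unpaired.**

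With equal variances, SD of change = SD × √(2(1 − r)), so the between-person SD = 0.9/√(2(1 − r)). The correlation r is not in the documents, so the values below are assumptions. Power is by exact t.

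| Assumed r | Between-person SD | Power, 15 per group | Power, 30 per group |
|---|---|---|---|
| 0.3 | 0.76 | 93.5% | 99.9% |
| 0.5 | 0.90 | 83.6% | 98.8% |
| 0.7 | 1.16 | 62.4% | 90.6% |
| 0.8 | 1.42 | 46.0% | 76.3% |
| 0.9 | 2.01 | 26.0% | 47.3% |

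The row r = 0.5 is the same as step 1. Below it the plan is over-sized; above it, under-sized at 15.

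**Step 4. Try 0.9 as the standard error of a difference between two groups of m.**

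SD = 0.9 × √(m/2). With an assumed m = 10, SD = 2.01, and power is 26% at 15 and 47% at 30. The documents mention neither a standard error nor groups of 10.

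**Step 5. How much room the recruitment target leaves.**

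Largest between-person SD that still gives 85% power by exact t, by number analysable per group:

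| Analysable per group | Largest SD (cmH₂O) |
|---|---|
| 15 | 0.88 |
| 20 | 1.03 |
| 25 | 1.16 |
| 30 | 1.27 |

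The last limit is 1.27/0.9 = 1.41 times the stated value.

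**What the steps show.** Of the readings tried, the stated 15 comes out only when the between-person SD is 0.9. The arithmetic itself therefore indicates how the authors used the figure.

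**The case for a change.** The strongest reply is that reproducing 15 shows how 0.9 was used, not what it is. The authors may have taken the SD of a within-person change from their publication and put it into a two-group formula. The result would look just as consistent, and power could be 62% or 46% at 15 per group. Nor is the larger recruitment a full answer: the surplus is set aside for attrition, subgroups and missing data, and even with 30 analysable per group 85% power is lost once the SD passes 1.27.

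Part of this stands. The documents leave the ± undefined and the Pcrit test unnamed, and the published source would have to be read to confirm what 0.9 measures. The extra recruitment is a partial buffer.

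The claim of harm does not stand. Nothing in the text says that the published ΔPcrit was a change within a person, and no correlation is given. The nearest context points the other way: ΔPcrit is introduced straight after a sentence about differences between groups, and is then restated as a difference at baseline. Loose shorthand for a target difference with a common SD fits both that wording and the number. The possible error also runs in both directions, since a pair-difference SD or r below 0.5 gives more power than claimed. Lastly, analysing subgroups takes nobody out of the main comparison, so only attrition and missing data use up the surplus.

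**Conclusion.** No change to the plan follows. The stated size is internally consistent: 15 per group for about 85% power follows from a difference of 1.0 and a common SD of 0.9 (86.1% by the normal formula, 83.6% by exact t). That rests on reading ± 0.9 as the between-person SD, which is the reading that both the arithmetic and the between-group wording support.

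The gap is one of labelling, and an analyst can fill it sensibly. The nature of 0.9 can be looked up in the authors' own published data, and the Pcrit test follows from how the controls were in fact matched: unpaired for group matching, paired for one-to-one. If the matching is one-to-one and 0.9 is the SD of the pair difference, power at 15 pairs is about 98%, so that choice does not endanger the aim.

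Enrolling more people, or re-estimating the SD part-way, would be a response to an SD that the documents give no reason to expect. With 30 per group recruited, a between-person SD up to 1.27 is tolerable if all are analysable, and up to 1.03 if only 20 are. Whatever the SD proves to be, the confidence interval for the Pcrit difference will show how much a null result excludes.

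### Aim 2a could, at little cost, also estimate whether the CPAP-minus-baseline change differs between MFS and controls, and use the randomised night order; neither is planned (minor improvement)

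*Combined protocol and SAP*

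**What the plan says.** - **Design.** Under Study Design/Protocol, participants are admitted "for a contiguous or separated two night stay". One night is the baseline polysomnography. The other is the physiology night on CPAP, where "nasal pressure will be titrated until non-flow limited breathing is achieved and UAO eliminated".
- **Night order.** The Randomization paragraph names the first-night effect as a possible confounder and therefore states that "the order in which participants are assigned to a baseline and physiology night study is randomized".
- **Aim 2a, within person.** "We will compare hemodynamics (heart rate and pulse pressure) at baseline vs CPAP in pair wise t-test comparisons".
- **Aim 2a, between groups.** Stratified regression is to determine "whether the magnitude of hemodynamic parameters are predicted by genotype (MFS vs non MFS) at baseline and CPAP". Both analyses are to account for sleep stage, body position and respiratory phase. Night order is not listed.
- **Aim 2a, sample size.** "required sample size of 15 in each group to see a difference of 10 units in hemodynamic parameters between groups at 90% power", with "a significance alpha level of 0.05". No standard deviation is given.
- **Aim 2b.** The plan will "explore the relationship between hemodynamic response to UAO and measures of aortic disease progression", but in MFS only, so it does not compare response between the groups.

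**The concern.** The two planned analyses answer two questions: does CPAP change heart rate and pulse pressure, and do MFS and controls differ in level at each condition? Neither estimates whether CPAP changes hemodynamics more in one group than in the other. The term stratified is not defined, but no reading of the text states a group-by-condition comparison.

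A reader who wants that answer can only set the two conditions, or the two groups, side by side and compare significance. That is not a valid test of a difference in change.

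Night order is randomised for a stated reason and then left out of the analysis. If the nights differ, order adds avoidable noise to every within-person change. A chance imbalance of order within a group also shifts that group's mean change.

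**Working it through.** **1. The plan's own figures.** Aim 1 gives a difference of 1.0, SD 0.9, 85% power and two-sided alpha 0.05. The normal approximation n = 2(1.960 + 1.036)² × 0.9² / 1.0² = 14.5 rounds up to 15, as stated. Aim 2 gives no SD, so its 15 per group cannot be reproduced, only solved backwards. Sidedness is not stated for Aim 2; two-sided is assumed, as in Aim 1. It is also not stated whether the 10 units is a difference in level on one night, a difference in change, or a paired difference. Using the t-test:

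- Level on one night: a two-sample test with n = 15 per group and 90% power needs a standardised difference of 1.226, so SD = 10/1.226 = 8.15. The SD of change is then 8.15 × √(2(1 − ρ)), where ρ is the night-to-night correlation. For assumed ρ of 0.3, 0.5 and 0.7 this is 9.65, 8.15 and 6.32.
- Difference in change: the SD of change is itself 8.15.
- Paired difference in 15 people: the SD of change is 11.1.

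**2. Precision and power for the group difference in change.** SE = SD of change × √(2/15) = SD of change × 0.365. The 95% CI half-width is 2.048 × SE (28 df). Power is from the noncentral t, ignoring any order effect.

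| Reading of the 10 units | SD of change | SE | CI half-width | Power, 10 units | Power, 5 units |
|---|---|---|---|---|---|
| Level, ρ = 0.3 | 9.65 | 3.52 | 7.2 | 78% | 28% |
| Level, ρ = 0.5 | 8.15 | 2.98 | 6.1 | 90% | 37% |
| Level, ρ = 0.7 | 6.32 | 2.31 | 4.7 | 99% | 55% |
| Change | 8.15 | 2.98 | 6.1 | 90% | 37% |
| Paired | 11.1 | 4.05 | 8.3 | 66% | 22% |

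If all 30 per group were analysed, the level reading gives 98% or more for 10 units and 51/65/85% for 5 units.

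**3. What the order term does.** Let p be the second-minus-first-night shift. A person's change moves by +p if CPAP comes second and by −p if it comes first, so 1:1 order adds p² to the variance of change. Example with ρ = 0.5 and p = 5: √(8.15² + 5²) = 9.56, giving SE 9.56 × 0.365 = 3.49 without the term and about 2.98 with it. Simulation with simple 1:1 order randomisation, which also carries the cost of estimating the term, gives 3.46 and 3.00. For ρ = 0.3/0.5/0.7 at 15 per group, the simulated change in SE from adding order is:

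| Assumed order effect | Group difference in change | Within-group CPAP comparison |
|---|---|---|
| None | about 2% larger | about 4% larger |
| 2.5 units | 1/3/5% smaller | 0.5% larger to 3% smaller |
| 5 units | 10/13/20% smaller | 8/12/19% smaller |

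With 5 units, power for a 10-unit difference rises from 68/79/91% to 76/89/98%. Type I error is about 5% with or without the term.

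**4. Chance imbalance.** If order is allocated by simple 1:1 randomisation (the method is not stated), the chance that a group of 15 splits 10:5 or worse is 2 × P(X ≥ 10), X ~ Bin(15, 0.5), which is 30%. With p = 5, a 10:5 split shifts that group's mean change by 5 × (10 − 5)/15 = 1.7 units.

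**5. Side-by-side reading.** These are simulations with 15 per group, SD 8.15, ρ of 0.5 and 0.7, and no true difference in change. A constant group difference of 5-7 units on both nights gives significance at one condition but not the other in 24-32% of trials. An identical 5-unit CPAP effect in both groups gives paired t-tests that disagree in 30-48%. The direct comparison of change keeps its 5% error rate.

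**The case against.** **The comparison may not be wanted.** The document gives only the statistics for the aims, not the full aims and hypotheses, so whether a group difference in change was ever of interest cannot be seen. A reader might infer that Aim 2a fails its own objective. The text does not support that, and the added comparison should be exploratory unless the sponsor declares it an objective. That point stands.

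**Order is already handled.** A reader might infer that leaving order out biases the CPAP comparison through the first-night effect. It does not: randomising order removes that systematic bias, and what remains is precision and chance imbalance. The plan also describes the first-night effect as one on sleep structure and already accounts for sleep stage, so only a residual effect on heart rate or pulse pressure counts. The documents give no size for it. An effect of 5 units is half the plan's target difference and may be generous; below about 2 units the term does almost nothing. This limits the benefit but does not remove it, because the cost when there is no order effect is only 2-4% in SE.

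**Power is poor for modest differences.** True: 22-55% for 5 units at 15 per group. On the level reading with ρ below 0.5, the difference in change is also less precise than a single-night comparison (78% against 90% power at ρ = 0.3). That argues for reporting an interval and against reading a non-significant result as equal response. It does not argue for leaving the estimate out.

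**Conclusion.** The point holds as a minor improvement. The text clearly shows that Aim 2a has no between-group comparison of the CPAP-minus-baseline change and no use of night order. The size of the gain is much less certain. It depends on the SD, the night-to-night correlation, the order effect and the meaning of the 10 units, and the documents give none of these.

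Under the three readings, power at 15 per group is 78-99%, 90% or about 66% for 10 units, and 28-55%, 37% or 22% for 5 units. The order term ranges from a 2% loss in the SE of the group difference in change to a 10-20% gain, the latter only if nights differ by about 5 units. The documents do not support a claim that the planned analyses are invalid, or that the sample size is wrong for what Aim 2a sets out to do.

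**What to change.** Add to Aim 2a, in substance:

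> For heart rate and pulse pressure, each person's CPAP-minus-baseline change, from values adjusted for sleep stage, body position and respiratory phase as already planned, will be regressed on group and night order. The within-group baseline-versus-CPAP comparison will include night order coded −0.5/+0.5. The planned MFS-versus-control comparisons at each condition are kept. The group difference in change will be reported with its 95% CI as an exploratory result, and a non-significant result will not be taken as evidence of equal response.

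Drop the exploratory label only if the comparison is declared an objective. If the matched controls of Aim 1 also serve Aim 2, the regression should reflect the matching; the power figures above treat the groups as independent. A mixed model with group, condition, their interaction and night order is an alternative. It may weight participants differently, so it is not interchangeable, and one approach should be named in advance.

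**Cost.** SAP wording and one extra regression per outcome, with no new participants, visits or measurements. If there is no order effect, the SE rises by about 2% for the difference in change and about 4% for the within-group comparison at 15 per group. Power for small differences stays low, so a null result could be misread unless the interval is shown.
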